The treatment device is classified as an “Exempt” device in accordance with the requirements of the international standard EN 62471 – Photobiological safety of lamps and lamp systems and, when used correctly, the output is less than the maximum permissible exposure (MPE) no special controls are needed for the environment it is to be used in. At the time of study implementation, the staff will be provided training on basic safety procedures relative to the use of the device. The staff will then virtually instruct the subject’s parent/guardian on the administration of the tPBM such that the headband is appropriately placed. The delivery of the tPBM is expected to last 10-40 minutes total (simultaneous application on the left and right forehead). The subject will be asked to rest for five minutes after the delivery of tPBM. Sites of application will be inspected at each study visit.

Subjects will be instructed to administer the treatment sessions daily for eight weeks, with each session lasting 10-40 minutes. Subjects will be instructed to contact the investigator or a member of his staff at any time between visits concerning adverse events or worsening of symptoms.

Following assessments will be performed at the Baseline Visit:

- CGI
- GAF
- CTAE
- Concomitant Medications
- ADHD-SC

Study Treatment: Virtual Clinical Monitoring Visits (Weeks 1-6)

There are 5 monitoring visits scheduled at Week 1, Week 2, Week 4 (Midpoint), Week 6, and Week 8.

Participants will be prescribed to administer study treatments at home daily for a period of 8 weeks. Study visits will have a visit window of +/- 3 days to facilitate scheduling.

During the visits, the participants will be asked questions about the symptoms of ADHD and ATs and general health in addition to any present side effects or changes in their medications. At weeks 2, 4 (Midpoint), and 6 the participant will be asked to fill out questionnaires.

Following assessments will be performed at the Week 1, Week 2, Week 3, and Week 6 Visits:

- CGI
- GAF
- CTAE
- Concomitant Medications
- TSRQ

Following assessments will be performed at the Midpoint (Week 4) Visit:

- CGI
- GAF
- CTAE
- Concomitant Medications
- ADHD-SC
- SRS-2

- BRIEF-P
- TSRQ
- CBCL

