1.2. Study Discontinuation

We will encourage subjects to continue enrollment in the study via follow-up visits regardless of the nature of discontinuation of the tPBM. At the end of the study, we will refer the subjects to their counselor and/or psychiatrist and will communicate clinical data upon signed authorization. If the CGI-S increases more than 2 points during the study, the subject will be counseled to start

or change to an FDA-approved medication treatment. If the CGI-S increases more than 5 points or if a subject becomes actively suicidal as per clinician judgment, termination from the study will be mandated. Subjects who are deemed actively suicidal and are in imminent danger will be escorted to Acute Psychiatric Service (the local psychiatric Emergency Department at Massachusetts General Hospital) for evaluation and subsequent hospitalization. If the subject is appropriate for outpatient monitoring, the subject will be followed with frequent appointments outside the study. Each subject will have the Investigator's contact information as well as instructions on how to call for emergency services, if needed.

If study participation is discontinued due to safety reasons, participants will receive three follow-up visits, while appropriate psychiatric follow up access is assured with their treating psychiatrist. If emergent suicidality were to occur during the course of the study, the supervising clinician will then directly assess the level of risk and take the appropriate action (including contacting treatment providers, working on a safety plan, arranging for emergency evaluation via an ER, calling 9-1-1, etc.). The clinician will document the actions taken, and it will be noted in the participant's file. Subjects who discontinue due to non-compliance with the protocol will receive a referral to treaters in the area.

A participant may withdraw consent at any time for any reason (e.g., lack of efficacy, adverse events, etc.). A subject may be withdrawn from the study by study staff at any time if any of the following conditions are met:

- Worsening of ATs, ADHD or current/emergent major psychiatric disorder.
- Subjects who experience intolerable adverse effects as determined by the PI.
- Emergent suicidality
- Pregnancy
- Failure to keep study appointments for more than 2 consecutive visits
- Failure to utilize the telemedicine platform
- Clinical judgment of the investigator

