Subjects may receive three clinical follow-up visits at the completion of the study (or if they are required to discontinue for safety reasons), allowing adequate time for appropriate psychiatric referrals to treaters in their communities. Follow-up visits are optional and are at no cost to participants. These visits are not part of the clinical trial and no research data will be collected during follow-up. Subjects who fail to keep study appointments or are non-compliant may be dropped from the study. These study subjects will be given a referral to treaters in their area but will not be offered three follow-up visits.

If a subject would like us to forward their clinical history to his/her primary care physician, or a new clinician, we will forward any pertinent information with the proper completed release of information authorization form. If a subject who has come from the clinic of the investigator happens to drop out of the study, he or she will return to his or her treating physician.

Study Assessment Scales and Forms

Subjects will be evaluated at scheduled intervals. At each visit, measures of safety and efficacy will be obtained using assessments of psychiatric symptoms and functioning (CGIs, GAF) and measures of adverse effects (CTAE). At the Midpoint (end of week 4) and Endpoint study visits (Week 8 or Endpoint), additional clinician-, subject-, and informant-rated assessments will be repeated (see below for details).

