dependent variable will be raw score on the SRS-2 Total scale and our predictor will be study visit (continuous). Secondary measures of efficacy for the treatment of ATs will be the SRS-2 subscales which include Awareness, Cognition, Communication, Social Motivation, and Restricted Interests and Repetitive Behavior. These subscales will also be analyzed using mixed-effects linear RMs predicting subscale score from study visit (continuous). Safety and tolerability will be assessed by examining adverse events reported throughout the trial.

Secondary Objective: posits that tPBM will be effective in the treatment of ADHD with ATs. The measure of efficacy for this objective will be the ADHD-SC which is collected at baseline, midpoint, and endpoint. We will examine the change in ADHD-SC score over time using a mixed-effects linear RM. Our dependent variable will be ADHD-SC score and our predictor will be the study visit (continuous).

Accountability/Investigational Product Control

U.S. federal law and ICH Guideline E6 § 5.14 requires that all investigational medical devices be strictly controlled. All study devices must be kept in a secured area at the clinical sites in compliance with all applicable FDA (U.S. sites) regulations.

The Principal Investigators or designated study site personnel who verify the receipt of the devices/device accessories must complete the Device/Accessories Acknowledgment Form and fax a copy to Niraxx, Inc. Device Accountability and Acknowledgment Logs will be maintained at study site. These logs will list all equipment received, the receiving date, the serial number of each device. Study site personnel will initial the log each time the device is used. Niraxx device use will also be recorded on the appropriate CRF.

Malfunctioning devices and device accessories, including all components, will be returned to Niraxx, Inc. for investigation, at Niraxx, Inc. expense.

VI. RISKS AND DISCOMFORTS

All adverse events will be recorded from the time of Informed Consent through study completion, or termination. The Adverse Event CRF must be completed and submitted to the IRB, as required. Regulations for adverse event handling and reporting contained in the FDA and ICH Guidelines will be adhered to.

Consideration of Adverse Events will hereafter consist of Adverse Events, Serious Adverse Events, and Adverse Device Effects, including Anticipated Adverse Device Effects and Unanticipated Adverse Device Effects.

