- ***Adverse Event*** is defined as any untoward/undesirable clinical occurrence in a clinical investigation of a subject using a device and/or product and which does not necessarily have a causal relationship with this treatment. An Adverse Event can therefore be any unfavorable and/or unintended sign, symptom, or disease temporally associated with the use of a device product, whether or not considered related to the device product. Only abnormal laboratory values that are deemed clinically significant by the investigator will be classified as adverse events.
- ***Serious Adverse Event*** is defined as any untoward/undesirable adverse experience that results in any of the following outcomes: 1) death; 2) a life-threatening adverse

experience; 3) inpatient hospitalization or prolongation of existing hospitalization; 4) a permanent/persistent or significant disability/incapacity or a congenital anomaly/birth defect; 5) important medical events that may not result in death, be life-threatening, or require hospitalization may be considered a serious adverse experience when, based upon appropriate medical judgment, they may jeopardize the subject and may require medical or surgical intervention to prevent one of the outcomes listed in this definition.

- ***Anticipated Adverse Device Effect*** is defined as any adverse effect related to the device or procedure, which is identified in the protocol.
- ***Unanticipated Adverse Device Effects*** is defined as any serious adverse effect on health or safety or any life-threatening problem or death caused by, or associated with, a device, if that effect, problem, or death was not previously identified in nature, severity, or degree of incidence in the investigational plan or application (including a supplementary plan or application), or any other unanticipated serious problem associated with a device that relates to the rights, safety, or welfare of subjects.

Potential Adverse Events

Risks to the subject may include but are not limited to the following:

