If skin erythema is present, treatment will be suspended. Patients will be instructed to contact the study site principal investigator or a member of his staff at any time between visits concerning adverse events or worsening of symptoms. If at any study visit the subjects' clinical condition is significantly worsened from baseline (operationalized as the clinical global impression improvement score, CGI-I, of 6 or higher) or if a subject becomes actively suicidal with intent and/or plan, based on the C-SSRS scale and/or the clinical interview, the subject will be offered to start an antidepressant medication. If the subject were deemed at imminent danger as a result of suicidality, s/he would be discontinued from the study and referred to appropriate clinical treatment (see 4.7.3 Study Discontinuation).

Photobiomodulation for ASD in ADHD

The Principal Investigator ([name]) will have weekly meetings which will include study RAs; during these meetings calls they will discuss all Adverse Event reports to identify any safety concern, based on such concerns they will be able to decide temporary discontinuation of study enrollment, modifications of the study protocol, or to terminate the study.

Research assistants responsible for data collection and storage will be aware of and comply with all regulatory requirements related to adverse events. In the event that a patient becomes ill or is injured as a direct result of study participation, medical care will be made available. All adverse events (and device events) will be followed to resolution and reported to the MGH IRB as serious in the event that 1. they are unanticipated and possibly related to the study (same reporting as SAE) or 2. if they meet any one of the following criteria: Any fatal event, immediately life-threatening event, permanently or substantially disabling event, event requiring or prolonging inpatient hospitalization, or any congenital anomaly. This also includes any event that a study investigator judges to impose a significant hazard, contraindication, side effect, or precaution.

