Study subjects will receive comprehensive clinical assessment of their psychiatric condition. This information will be readily available to their counselors if the subjects agree to disclose. This information might guide counseling in the long term treatment. In the short-term, the subject will receive close and systematic monitoring, beyond current standards of care. Easy access to routine appointments are also a potential benefit in the community population, which is often underserved. The subjects will have access to a different modality of treatment if counseling was not sufficient and if medications were not acceptable to them. However, there may be no improvement at all, or benefit to participant.

IX. MONITORING AND QUALITY ASSURANCE

Consistent with good clinical practice, safety will be monitored at each study visit by a subject's assigned clinician. This clinician will be available 24 hours a day by page. The principal investigator will supervise all study activities including ratings and reported adverse events. All procedures have been designed to minimize subject discomfort, and no subject will be asked to engage in research procedures not outlined in the consent form.

If a subject is withdrawn from the study due to adverse events, lack of response, or as a decision by the clinician, they will be offered open treatment for three months, giving adequate time for appropriate psychiatric care to be arranged.

Safety will be monitored through treatment-emergent adverse events. Subjects will be monitored for adverse events at each visit. All adverse events will be recorded. A subject may be dropped from the study or dosage may be decreased at any time due to adverse events. All adverse events will be reported to the PHRC according to PHRC guidelines. All concomitant medications will be assessed at every study visit.

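### No stated mechanism records the outcome of adverse events still open when a participant leaves the study, or of an on-study pregnancy, although events must be followed to resolution

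*Combined protocol and SAP*

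**What the plan says.** All references are to the combined protocol and SAP.

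- **Duty to follow.** Safety Monitoring: "All adverse events (and device events) will be followed to resolution". Reporting Procedures for All Adverse Events lists the outcome, and the resolution date where one applies, among the attributes to be entered on the CRF.
- **Recording window.** Risks and Discomforts: "All adverse events will be recorded from the time of Informed Consent through study completion, or termination".
- **Visits after exit.** Section 1.2, Study Discontinuation, provides three visits when participation ends for safety reasons. It then says "Follow-up visits are optional and are at no cost to participants" and "These visits are not part of the clinical trial and no research data will be collected during follow-up".
- **Stopping treatment only.** The same section opens: "We will encourage subjects to continue enrollment in the study via follow-up visits regardless of the nature of discontinuation of the tPBM".
- **Exit visit.** Withdrawal from the Study lists an exit visit, where feasible, with the adverse-event log (CTAE) and a virtual examination of the exposure sites.
- **Pregnancy.** Section 1.2 and Withdrawal from the Study both list pregnancy as a possible reason for withdrawal. The definition of a serious adverse event includes "significant disability/incapacity or a congenital anomaly/birth defect".
- **Site inspection.** Baseline Visit (Week 0): "Sites of application will be inspected at each study visit". Table I marks this examination from Baseline to Week 8. Neither Table I nor the Week 10 visit list has it at Week 10.
- **A further provision after withdrawal.** Monitoring and Quality Assurance says of participants withdrawn for adverse events, lack of response or by clinician decision that "they will be offered open treatment for three months".

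**The concern.** Read literally, the duty to follow an event outlasts the permission to record it. Study clinicians may see a withdrawn child up to three more times while the event is still running, and those visits are declared free of research data. Staff who want to meet the follow-up duty have no instruction on where the outcome goes.

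This matters because safety is a primary objective of a single-arm paediatric trial with about 60 exposed participants, and the protocol acknowledges that long-term effects are unknown. The affected participants are not a random subset. They are those who leave with an unresolved event, so the missing durations and outcomes would concern the events that weigh most in a safety conclusion.

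**Working it through.** The plan gives no figure on this point, so the check is mainly a comparison of passages.

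**1. Who is affected?** Stopping tPBM is not the same as leaving the study. A participant who stops treatment but stays enrolled still has the CTAE at every visit to Week 10 (Table I). The question arises only when study participation ends with an event unresolved.

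**2. Does the plan itself cause such exits?** Yes. Section 1.2 mandates termination for active suicidality, or for a CGI-S rise of more than 5 points, and places outpatient monitoring outside the study. The risk paragraph on depression, suicidality and manic switch discontinues participants with active suicidal ideation, mania or hypomania. Safety Monitoring discontinues those in imminent danger from suicidality. The text on event intensity adds withdrawal at the investigator's judgment.

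**3. What can record the outcome after exit?**

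| Route | Where | Limit |
|---|---|---|
| Exit visit with CTAE | Withdrawal from the Study | Where feasible; shows status at exit only |
| CTAE form | Section 1.2.1.2 | Defined for tPBM-related events during the study |
| CRF fields for outcome and resolution date | Reporting Procedures | Fields exist, but the recording window closes at termination |
| Outcome in reports to the IRB | Safety Monitoring | Serious events; no later update schedule |
| Supervised care until symptoms resolve | Text on event intensity | Clinical care; no recording stated |
| Follow-up information on request | Withdrawals for Adverse Events | Discretionary |
| Three follow-up visits | Section 1.2 | Optional, outside the trial, no research data |

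These routes are partial. None is a stated, systematic way to record the outcome after exit.

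**4. Pregnancy.** The three visits mentioned under Screening Process follow a positive test before any exposure, so they do not bear on this point. For a pregnancy found during treatment, no section describes follow-up. Study Design allows at most 14 weeks from enrollment, and Week 10 falls 14 days after Week 8. A congenital anomaly would ordinarily become known only after that window.

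**5. Size.** Sample Size aims for 60 exposed participants; its enrollment figure reproduces as 60 / (1 − 0.33) = 89.6, rounded up to 90. The documents give no rate of withdrawal for adverse events. For an assumed rate p, the expected number is 60p and the chance of at least one is 1 − (1 − p)^60:

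| Assumed p | Expected number | Chance of at least one |
|---|---|---|
| 1% | 0.6 | 45% |
| 3% | 1.8 | 84% |
| 5% | 3 | 95% |
| 10% | 6 | 99.8% |

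These are upper bounds for each p, because some events will have resolved by exit and some outcomes may be captured by the partial routes.

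**The case against.** The best defence is that the passages can be read together. The recording window may be meant for new events, and the follow-up duty for events already recorded; that duty carries no end date. The three visits serve referral to community care, and nothing says that they are the route for adverse-event follow-up or that other routes are barred. The documents' own experience also suggests few such exits: the open-label pilot in 10 adults reported no treatment-limiting or serious events, and each listed device effect was reported by under 0.1% of subjects and users.

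Much of this stands, and it rules out stronger readings that a reader might infer:

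- **That the outcomes are lost.** The partial routes above remain, so the text shows a missing mechanism and not certain loss.
- **That every event ending treatment is affected.** Continued enrollment after stopping tPBM is encouraged.
- **That any pregnancy is affected, or that a congenital anomaly could never be observed.** A pregnancy found at screening is unexposed. Withdrawal for an on-study pregnancy is listed as possible, not automatic. All serious events that become known must be reported to the IRB.
- **That a Week 8 skin reaction goes unfollowed.** The Week 10 visit has the CTAE and the TSRQ; only the wording on inspection conflicts.

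What the defence does not supply is an instruction on where an outcome learned after termination is recorded. The harmonised reading has to be inferred, and the explicit bar on research data points the other way.

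**Conclusion.** The concern holds for two groups: participants who leave the study with an unresolved adverse event, and participants with an on-study pregnancy after device exposure. For the first, the follow-up duty, the recording window and the status of the follow-up visits do not agree. For the second, no follow-up is described.

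The number affected cannot be taken from the documents. The bound of about 0.6 to 6 participants rests on an assumed 1% to 10% of 60 leaving for an adverse event, and on every such event being open at exit with no other capture. A count of several participants should not be read as a prediction.

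Two smaller inconsistencies sit alongside. Inspection at each study visit does not match the Week 10 schedule. The provisions after withdrawal also differ: section 1.2 describes the three visits both as something participants will receive and as optional, and Monitoring and Quality Assurance offers three months of open treatment. A count of visits and a period of care are not strictly incompatible, but the text should be aligned. The efficacy analysis and power are not affected.

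**What to change.** - Amend section 1.2 and the recording window in Risks and Discomforts to agree with Safety Monitoring. Adverse events open at termination should continue to be recorded on the existing adverse-event form to resolution, including from information obtained at the follow-up visits.
- State that the outcome of any on-study pregnancy with device exposure is recorded, with consent.
- Reconcile the Baseline Visit wording on site inspection with the Week 10 list and Table I, for example by adding the virtual examination to the Week 10 video visit.
- Reconcile section 1.2 with Monitoring and Quality Assurance on what a withdrawn participant is offered. Which provision applies is for the sponsor and investigator to decide.

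The cost is small: protocol and consent wording, adverse-event records that stay open longer, and a later contact for a rare pregnancy. The form exists, and the follow-up visits are already offered.
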